A Randomized Trial of Transcutaneous Nerve Stimulation for Neurogenic Bladder Patients

[name]

NCT 02582151

March 1 2016

Specific Aim

To determine the efficacy of transcutaneous tibial nerve stimulation (using skin patch electrodes) for the treatment of patients with neurogenic bladder symptoms.

Hypothesis

We hypothesize that the study protocol of transcutaneous tibial nerve stimulation performed at home during 30 minute sessions, 3x/week, for 12 weeks will be associated with a statistically significant improvement in neurogenic bladder symptoms.

Background: Significance & Innovation

A variety of neurologic diseases can lead to bladder dysfunction, including multiple sclerosis, Parkinson's disease, stroke, dementia, cerebral palsy, and spinal cord injury(1). This neurogenic associated bladder dysfunction significantly impacts patients quality of life(2,3). Treatment consists of conservative measures, and often the use of anticholinergic medications. Anticholinergic medications have been primarily studied for the more common indication of overactive bladder(4). In small clinical trials and case series, these medications have demonstrated improvements in urgency incontinence, and urodynamic parameters (such as bladder capacity and detrusor pressure) among neurogenic bladder patients(5). However, anticholinergic medications have a number of undesirable side effects, including dry mouth, constipation and cognitive changes(5,6). This is particularly bothersome in the neurogenic population which commonly use other medications associated with dry mouth(7), have neurogenic constipation(1) and have existing cognitive impairments. These anticholinergic side effects have been shown to significantly limit medication compliance among both the general population(8), and neurogenic bladder patients(9). Even with anticholinergic medications, many patients have residual and bothersome urinary symptoms(3). The recently introduced mirabegron is an alternative oral medication that works through stimulation of the beta 3 receptor in the bladder(10), and studies are underway evaluating its efficacy in the neurogenic bladder population.

Neurogenic bladder patients who find anticholinergics ineffective or intolerable are a challenging population to treat. The recently updated European Association of Urology guidelines for neurogenic bladder list intradetrusor onabotulinumtoxinA and sacral neuromodulation as potential treatment options for neurogenic bladder patients. While onabotulinum toxin injection is well established and commonly used for neurogenic bladder dysfunction(11), it is not appropriate if a patient is unable or unwilling to perform self catheterization in the event of urinary retention. The risk of urinary retention is considerably higher among patients with neurogenic dysfunction(12) compared to the overactive bladder population. The side effective profile and limited efficacy of anticholinergics, and the potential risk of catheterization with intravesical onabotolinium toxin creates a need for neuromodulation treatment modalities.

Neuromodulation of the lower urinary tract has been studied for over a century(13). The application of low level electrical energy either directly to the sacral nerve roots, or through a peripheral nerve originating from the sacral spinal cord, is thought to mediate somato-visceral interactions within the sacral spinal cord, reset somatic afferents and modulate the micturition reflex(13). The ability of sacral neuromodulation to prevent neurogenic bladder systems in the acute setting of a spinal cord injury has been reported(14), and this underscores importance of studying neuromodulation in patients with neurologic disease.

One form of neuromodulation is percutaneous tibial nerve stimulation, which involves placing a small needle above the medial malleolus in order to directly stimulate the posterior tibial nerve. In animal

models, the stimulation of the tibial nerve has been shown to suppress detrusor overactivity(15), and to alter neuronal metabolic activity in the sacral spinal cord(16). The exact mechanism of action in humans is poorly understood, however there is evidence that percutaneous tibial nerve stimulation can modify the somatosensory pathway(17), and alter urodynamic parameters(18) in humans.

The clinical evidence for the efficacy of percutaneous tibial nerve stimulation for overactive bladder has been well reviewed in a recent systematic review and the AUA/SUFU overactive bladder guidelines(19,20). Variable definitions of success have been used (such as clinical parameters, urodynamic outcomes, and validated patient reported outcome measures), with general success rates of 55-80% after 3 months of treatment, and evidence of efficacy up to 3 years with a monthly maintenance protocol(21). The RCT evidence is summarized in Table 1 below. Across all clinical trials and the systematic review, no serious treatment related adverse effects were seen, and minor adverse events were limited to transient skin irritation, leg cramps or toe/foot pain.

In summary, neurogenic bladder symptoms often have a significant impact on a person's quality of life. A large proportion of people are not well treated with anticholinergic medications, and may not be candidates for intravesical onabotulinum injection. Tibial nerve stimulation is a minimally invasive form of neuromodulation which may be a potential effective treatment, however there is a lack of high quality evidence to support this option. Transcutaneous delivery of electrical current with patch electrodes may be an effective means of tibial nerve stimulation that allows the patient to have the convenience of an at home treatment schedule, with very low associated costs. The objective of this study is to conduct a pilot randomized, sham-controlled, clinical trial to assess the short-term effectiveness of transcutaneous posterior tibial nerve stimulation for patients with neurogenic bladder symptoms that are not adequately controlled with pharmacologic therapy.

Design and methodology

Study design: This is a randomized, double-blind, sham-controlled, clinical trial. The primary intervention is 30 minute sessions, 3x/week, for 12-13 weeks of transcutaneous tibial nerve stimulation sessions carried out at home. The sham intervention will consist of the same treatment schedule, except with the application of transcutaneous nerve stimulation to the lateral aspect of the lower leg, away from the tibial nerve. Patients will undergo a 12-13 week treatment course. The patient and the treating physician will be blinded to the group assignment of the patient. Randomization will be done using a random number generator, and study assignment will only be released at the end of the study. Only the study nurse instructing the patient on placement of the study electrodes will know the patient assignment. The effectiveness of our sham protocol will be evaluated with a question during week 2-3 asking if they think they are in the active or sham group. The study visit schedule is outlined in figure 1.

Figure 1. Proposed study schedule

STUDY SCHEDULE	Visit 1 Screening	Visit 2 Randomization	Telephone Followup	Visit 3 End of study
Visit Windows	1- 4 weeks prior to Randomization	Week 0	Every 2-3 Weeks	12-13 Weeks
Documentation of Consent	X			
Medical History and Physical Exam	X			
Inclusion/ Exclusion Criteria Review	X			
Medication and Health Review	X			X
Urine Pregnancy Test	X			
PPBC Questionnaire	X		X (week 6-7 only)	X
Qualiveen-SF/NBSS Questionnaire	X			X
3 day Voiding diary	Diary Provided	Completed Diary Returned & Provided for Visit 3		Completed diary returned
24hr Urinary Pad test	Supplies Provided with instruction	Pads Returned & Provided for Visit 3	Pad test done 1-7 days prior to visit 3	Pads Returned
Randomization		X		
Initial 30 minute treatment session in clinic with nurse supervision		X		
Assessment of treatment masking			X (week 2-3 only)	
Assessment of compliance, review instructions, address any adverse events or questions			X	
Physician assessment of benefit				X

Inclusion criteria

1. >18 years of age, with a clinical condition associated with neurogenic bladder dysfunction (multiple sclerosis, Parkinson's disease, stroke, dementia, cerebral palsy, spinal cord injury)(27).
2. Failure of behavioral measures and/or pharmacologic therapy to adequately control neurogenic bladder symptoms.

Exclusion criteria

1. Current or previous percutaneous/transcutaneous tibial nerve stimulation or sacral neuromodulation therapy
2. Stress predominant urinary incontinence
3. Newly added bladder medication or dose change with the last 2 months (Tamsulosin, Silodosin, Alfuzosin, Terazosin, Baclofen, Diazepam, amitriptyline, imipramine, DDAVP, tolterodine, oxybutynin, fesoterodine, darifenacin, solifenacin, trospium, mirabegron)
4. Intravesical botulinum toxin use within the last 1 year
5. Implanted pacemaker or defibrillator
6. History of epilepsy
7. Unable or unwilling to commit to study treatment schedule
8. Pregnant, or possible pregnancy planned for the duration of the study period
9. Active skin disease of the lower legs (dermatitis, cellulitis, eczema, trauma)
10. Documented allergy to patch electrodes or their adhesive
11. Metallic implant within the lower limb

Intervention: Transcutaneous electrical nerve stimulation is a safe and effective therapy that has been used by physicians and other health professionals for a variety of conditions such as pain and muscle

rehabilitation(28,29). Two adhesive patch electrodes will be applied to one of the patient's lower limb, and the location used will be based on their treatment assignment (active treatment versus sham). The initial treatment will be carried out in the clinic under the supervision of the investigating physician, with training provided for the patient on proper use of the device by the study nurse. The remaining treatments will be detailed on a calendar for the patient, with telephone contact every 2-3 weeks with research staff to assess compliance. When undergoing active treatment, patients will have the electrodes applied posterior to the medial malleolus, and 5-10 cm above the medial malleolus of the same leg, just behind the medial tibial edge. As per previous studies involving transcutaneous posterior tibial nerve stimulation for neurogenic bladder and overactive bladder(30-33) and similar to percutaneous tibial nerve stimulation(26), we will use the bipolar stimulation setting, with a frequency of 10 Hz, 200ms pulse, and the amplitude will be titrated up to patient's maximum non-painful tolerance or toe twitch in the case of complete SCI(30) (between 0.5-20mA). For patients undergoing sham treatment, they will have the patch electrodes placed on the lateral side of the lower limb, and instructed to keep the current setting stable at 1mA. This will prevent any meaningful stimulation of the tibial nerve, while still delivering a slight tingling sensation to simulate active treatment.

Primary outcome measure: We will use Patient Perception of Bladder Condition question, which is a common used endpoint in overactive bladder studies. Although it has not been formally studied in neurogenic bladder, its face validity is high, and it has been used for this purpose in the past(34). It is an ordinal scale from 0-5 ("My bladder does not cause me any problems at all" to "my bladder causes me many severe problems"). In the general population it is a valid, reliable and responsive single question(35). Patients will be categorized as responders (score improvement by 2 points between screening visit 1 and end of study visit 3) or non-responders.

Secondary outcome measures:

1. Neurogenic bladder symptom score (NBSS): valid and reliable tool for assessing neurogenic bladder symptoms(36).
2. The Qualiveen-SF is a measure of neurogenic bladder related QOL, which has been specifically shown to valid, reliable and responsive in neurogenic bladder(37,38).
3. 3-day voiding diary parameters (daily voiding frequency, functional bladder capacity, mean voided volume, longest time between voids, nocturia, number of urgency incontinence episodes). This is a valid and reliable measure of urinary symptoms(39).
4. Quantification of urinary incontinence with 24hr pad weights. This is stable, reliable and responsive measure of the degree of urinary incontinence(40,41), and will be analyzed for the subgroup of patients with incontinence.
5. Physician assessment of benefit will be completed based on a standard clinical history at study visit 3 (end of study), and graded on a 7 point global response assessment.

Sample size: Using previous percutaneous tibial nerve stimulation studies as a guide(26), we estimate 20% of sham patients and 60% of actively treated patients will be responders. Using the Chi-square test, a two-sided alpha of 0.05, and 80% power, 27 patients per group will be required. Our final sample size, adjusting for a 10% dropout rate, is 60 (30 per group). Our sample size calculation is based on our intention to treat analysis.

Statistical Analysis: Analysis of our primary outcome will be an intention to treat analysis (using the chi squared test) based on the proportion of patients classified as a responder using the change in the patient perception of bladder condition. A secondary analysis, based on a per protocol analysis (for efficacy) will be performed for patients who completed at least 80% of the treatment sessions for at least 20 min each (determined from patient completed treatment diary, and electronic usage log in the TENS device). Secondary endpoints will be analyzed as appropriate using the students t-test or chi squared test. All data analysis will be carried out using SAS 9.2.

References

2. Ku JH. The management of neurogenic bladder and quality of life in spinal cord injury. *BJU Int*. 2006 Oct;98(4):739–45.
4. Ouslander JG. Management of overactive bladder. *N Engl J Med*. 2004 Feb 19;350(8):786–99.

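### The allocation scheme is not specified and the primary test ignores diagnosis: stratified blocks with a matching test would be a cheap improvement, not the repair of an error

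*Combined protocol and SAP*

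**What the plan says.** On allocation, the Study design paragraph (Design and methodology) says: "Randomization will be done using a random number generator", with assignments disclosed only once the study has ended. It adds: "Only the study nurse instructing the patient on placement of the study electrodes will know the patient assignment". No allocation ratio, sequence type, block size, stratification factor or minimisation appears anywhere in the document.

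The Inclusion criteria admit patients with any of six conditions: "multiple sclerosis, Parkinson's disease, stroke, dementia, cerebral palsy, spinal cord injury". The expected case mix is not given.

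The Sample size paragraph assumes that "we estimate 20% of sham patients and 60% of actively treated patients will be responders", and continues: "Using the Chi-square test, a two-sided alpha of 0.05, and 80% power, 27 patients per group will be required". It then allows for dropout and arrives at 60 patients, 30 in each arm, which implies 1:1 allocation.

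The Statistical Analysis paragraph begins: "Analysis of our primary outcome will be an intention to treat analysis (using the chi squared test"). It mentions no adjustment for diagnosis or any other baseline variable.

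**The concern.** Neither the allocation nor the primary analysis, as written, takes account of case mix. In a trial of 60 patients, chance alone can place noticeably more of one diagnosis in one arm. If diagnosis is related to response, the observed responder difference moves with it, and the unadjusted test has no means of separating the two.

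There is some reason to think that diagnosis may matter here. The Intervention section uses a different end point for current titration in complete spinal cord injury. The sham relies on the patient feeling a mild sensation. The primary outcome is one self-rated item that the protocol acknowledges has not been formally studied in neurogenic bladder.

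At stake are a little precision and the credibility of a single small result: a lopsided diagnosis table invites challenge whichever way the trial comes out.

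**Working it through.** **1. The plan's own figure.** Inputs from the Sample size paragraph: 20% v 60%, two-sided alpha 0.05, power 80%, so the mean proportion is 0.40 and the difference is 0.40.
- Uncorrected: n = [1.96 × √(2 × 0.4 × 0.6) + 0.842 × √(0.2 × 0.8 + 0.6 × 0.4)]² / 0.4² = (1.358 + 0.532)² / 0.16 = 22.3, so 23 per group.
- Continuity-corrected: (22.3/4) × [1 + √(1 + 4/(22.3 × 0.4))]² = 27.1, which is 28 rounded up or 27 rounded to the nearest. The exact power of the Yates-corrected test at 27/27 is 80.2%.
- Dropout: 27/0.9 = 30 per group, 60 in all.

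The plan's figures reproduce with a continuity correction.

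**2. Arm sizes if allocation is simple 1:1 (assumed).** One arm's size is Binomial(60, 0.5), with SD √15 = 3.9.
- P(exactly 30:30) = 10.3%
- P(24:36 or worse) = 15.5%
- P(22:38 or worse) = 5.2%

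Power at 20% v 60%, taking the worse direction of each split:

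| Split | Uncorrected formula | Exact, Yates-corrected |
|---|---|---|
| 30:30 | 90.6% | 85.1% |
| 24:36 | 89.3% | 82.5% |
| 22:38 | 88.3% | 82.5% |
| Average over all splits | 90.1% | 84.7% |

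The average loss is 90.6 − 90.1 = 0.5 point, or 85.1 − 84.7 = 0.4 point with the correction. These figures are for all 60 patients. With 54 evaluable, the uncorrected figures are 87.3% at 27:27 and 85.9% at 22:32.

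**3. Balance of diagnosis.** Case mix is not documented, so the counts are assumptions.
- 20 patients with one diagnosis, simple allocation: Binomial(20, 0.5) gives 13:7 or worse in 26.3% of trials and 14:6 or worse in 11.5%.
- 10 patients: 7:3 or worse in 34.4%. With six diagnoses of 10 each, at least one does so in 1 − (1 − 0.344)⁶ = 92%.
- With the arms fixed at 30:30 but no strata (hypergeometric), the 14:6 figure falls to 5.4%, but the 7:3 figure falls only to 30%. Equal arms alone do not balance diagnosis.

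**4. Effect of a 14:6 split on the observed difference, with no treatment effect.** In arms of 30 the shift is (14 − 6)/30 × gap in responder rates. The gap is not documented.
- Gap 30 points: 0.267 × 30 = 8.0 points
- Gap 10 points: 0.267 × 10 = 2.7 points

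Under simple allocation the arms need not be equal. If the other 40 patients split 20:20, the arms are 34 and 26, and the shift for a 30-point gap is (14/34 − 6/26) × 30 = 5.4 points. Eight points is therefore towards the high end. For scale, the ordinary standard error of the difference at 20% response and 30 per arm is √(2 × 0.2 × 0.8/30) = 10.3 points.

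**5. What stratification and a matching test would gain.** Simulation of 200,000 trials under assumed inputs: 20 patients with 40% sham response and 40 with 10% (overall 20%), and 40 points added on active treatment in both groups.

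| Allocation and test | Power |
|---|---|
| Simple, unadjusted chi-squared | 90.3% |
| Simple, Cochran-Mantel-Haenszel | 92.7% |
| Exactly balanced strata, Cochran-Mantel-Haenszel | 93.4% |

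Type I error is 5.2% for the first row and about 5% for the last. The full change gains 93.4 − 90.3 = 3.1 points. Over the assumptions tried, from diagnosis not prognostic to gaps of 20 to 30 points, the gain ran from about 0 to 4 points.

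**The case against.** A random number generator is a tool, not a sequence type. The same tool can produce permuted blocks or a fixed 30:30 list, and the stated 30 per group fits such a list at least as well. A reader might infer that the protocol has chosen simple randomisation and so fails to deliver its own sample size. The documents do not support that: they neither state nor exclude a restricted list. This part of the objection stands in full, and the arm-size figures above are conditional for that reason.

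A reader might also infer that the six diagnoses respond very differently. The documents give no responder rates by diagnosis. The one diagnosis-specific element is the titration end point for complete spinal cord injury. That stands too, so the effect of imbalance can be given only as a range.

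The strongest statistical objection is that randomisation makes the comparison unbiased on average, and that chance imbalance is already allowed for in the test's error rate. Even under a 30-point gap, the planned test keeps about 5% type I error and about 90% power. The shift in question is smaller than one standard error. The protocol's background also calls the trial a pilot. All of this is correct. It rules out calling the plan invalid or biased, but it does not remove the case for a slightly better method at almost no cost.

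Finally, most of the gain in the simulation comes from the adjusted test alone (2.4 of the 3.1 points). An unstratified blocked list with a pre-specified adjusted analysis is therefore a reasonable alternative.

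**Conclusion.** This holds as a cheap improvement, not as an error in the plan. The document leaves the allocation scheme unspecified, and neither design nor primary analysis, as written, deals with a case mix of six diagnoses.

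Uneven arm sizes matter little: about 0.5 point of power, with every split from 22:38 to 38:22 above the planned 80% when all 60 patients are analysed. The sample size stands, and unequal arms do not invalidate a chi-squared test.

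The better reason to act is protection of one small trial against a lopsided diagnosis mix, plus a gain of about 0 to 4 points of power. The low end applies if diagnosis does not predict response. These sizes rest on an assumed case mix, assumed gaps between diagnoses and, for the imbalance probabilities, simple allocation. None of the three is given in the documents.

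**What to change.** Replace the randomisation sentence with a statement that allocation is 1:1 from a computer-generated list in permuted blocks of varying, undisclosed size (for example 4 and 6), stratified by two or three grouped diagnoses (for example spinal cord injury / multiple sclerosis / other). In the Statistical Analysis paragraph, replace the unadjusted primary test with a Cochran-Mantel-Haenszel test over the same strata, keeping the intention-to-treat population.

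The cost is a different list and a few sentences. Diagnosis is already established at screening, and no extra patients or staff are needed. There are three downsides:
- Blocks can make some assignments guessable, particularly to the nurse who sees each one. Varying, undisclosed sizes limit this.
- Small strata leave incomplete blocks, so the number of strata must stay at two or three, and an exact 30:30 split is no longer guaranteed.
- The remaining group still pools several diagnoses, and imbalance within it is not controlled. The grouping should be settled against the clinic's expected case mix.

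### The plan names two different supervisors for the first treatment session, and a physician who watches it would learn the arm and might then give the visit 3 rating

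*Combined protocol and SAP*

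**What the plan says.** The first treatment session, at visit 2, is described in two places under Design and methodology.

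- Figure 1 lists it as "Initial 30 minute treatment session in clinic with nurse supervision".
- The Intervention paragraph says "The initial treatment will be carried out in the clinic under the supervision of the investigating physician", and continues "with training provided for the patient on proper use of the device by the study nurse".

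The Study design paragraph, which calls the trial double-blind, sets the blinding rules:

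- "The patient and the treating physician will be blinded to the group assignment of the patient".
- "Only the study nurse instructing the patient on placement of the study electrodes will know the patient assignment".
- "study assignment will only be released at the end of the study".

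The Intervention paragraph ties electrode position to the arm: "the location used will be based on their treatment assignment (active treatment versus sham". For active treatment, "patients will have the electrodes applied posterior to the medial malleolus, and 5-10 cm above the medial malleolus of the same leg"; for sham, the electrodes go on the outer side of the lower leg. Current handling also differs: it is titrated in the active arm and held at 1 mA in the sham arm.

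Item 5 of the secondary outcome measures is a physician's assessment of benefit at visit 3, on a seven-point global scale. The rater is identified only as a physician.

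**The concern.** One session has two named supervisors, and the difference bears on blinding. The arm can be read from the patient's leg, and probably also from how the current is set. A physician who supervises in the ordinary sense of watching the set-up would therefore know the assignment, which the Study design paragraph reserves to the nurse.

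What is at stake is item 5. It is a subjective judgement drawn from the clinical history, the kind of outcome most open to influence from knowing the arm. If the physician present at visit 2 also gives that rating, it is not blinded, although the plan presents the trial as double-blind. The only masking check described asks patients, at week 2-3, which group they think they are in. It would not detect an unblinded physician.

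**Working it through.** The point rests on comparing passages; the only arithmetic is a count of the ratings that could be exposed.

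1. **Supervisor.** Figure 1 says nurse. The Intervention paragraph says investigating physician, with the nurse training the patient. Both describe the initial in-clinic session.

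2. **Is the arm visible at that session?** Yes. Electrodes are on the inner ankle and lower leg (active) or the outer side of the leg (sham). Titration against a fixed 1 mA is a second cue.

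3. **Is this the main opportunity to see it?** Yes. It is the only treatment session scheduled in clinic; the rest are done at home.

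4. **What follows, and on what conditions?**
   - (a) If supervising includes seeing the electrodes, the rule that only the nurse knows the assignment fails.
   - (b) If (a) holds and the investigating physician is also the treating physician, the physician-blinding rule fails.
   - (c) If (a) holds and that physician gives the visit 3 rating, item 5 is unblinded.

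   The documents settle none of these. They use the terms investigating physician, treating physician and physician assessment without saying whether these are the same person.

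5. **Which outcomes are exposed?** Of five secondary outcomes, four are not physician-rated: the symptom score, the quality-of-life score, the voiding diary and the pad weights. Item 5 is physician-rated, so 1 of 5 is directly exposed. The primary outcome is the patient's own perception of bladder condition.

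6. **How many ratings?** The Sample size paragraph requires 27 per group and allows for 10% dropout: 27 / (1 − 0.10) = 30 per group, or 60 in total, which reproduces the planned total. Expected visit 3 ratings are therefore 60 × 0.90 = 54 (30 × 0.90 = 27 per group). The number affected runs from 0 (the physician does not see the electrodes, or someone else rates) to 54 (one supervising physician, or several, saw every set-up and rated the same patients).

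The documents give no figure for the size of any resulting bias, and none is modelled here.

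**The case against.** The strongest reply is that the two supervision statements describe two layers: the physician is responsible for the visit, and the nurse runs the session. Both passages give the nurse a hands-on role. The Intervention paragraph never says that the physician places electrodes, watches placement, sets the current or is told the arm. Read in the light of the explicit blinding rules, general oversight leaves the physician blinded. The effect on an outcome then needs two unproven facts, and the 0 to 54 range only spans none to all.

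Much of this stands. The oversight reading is possible, the documents do not show that blinding is broken, and the range is a bound that says nothing about likelihood. The rule on releasing assignments at the end of the study also adds little, since the nurse must know the arm at visit 2.

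The reply does not dispose of the point. Nothing in the plan keeps the supervising physician from seeing the electrodes, and nothing separates that physician from the visit 3 rater. Site staff who follow the Intervention paragraph in its natural sense would breach the rules in the Study design paragraph.

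**Conclusion.** The concern holds. The plan's statements on who supervises the first session differ, and the natural reading of the Intervention paragraph conflicts with the plan's own blinding rules. The consequence is conditional: item 5 loses its blinding only if the supervising physician sees the electrodes or device settings and also rates benefit at visit 3. The direct reach is then one of five secondary outcomes and at most 54 expected ratings, assuming the planned 10% dropout. The primary outcome could be touched only indirectly, for instance if an unblinded physician cued the patient, and no such effect is claimed. This should be fixed because a subjective outcome may be exposed and the remedy is cheap.

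**What to change.** - Reconcile the Intervention paragraph with Figure 1 and the Study design paragraph on who supervises the first session and who is in the room.
- State who rates benefit at visit 3.
- State that this rater, and any physician described as blinded, does not attend electrode placement or current titration and does not see electrode site or device settings.
- If a physician does oversee placement, amend the sentence that reserves knowledge of the assignment to the study nurse. Where existing staff allow, have a different physician rate at visit 3; otherwise report item 5 as unblinded.

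The cost is wording plus minor task allocation at visit 2. No extra staff are required, because reporting the rating as unblinded is the fallback. The sample size and the primary analysis do not change.

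### Response requires a 2-point fall on the 0–5 PPBC, but eligibility sets no minimum score, so a patient screening at 0 or 1 cannot respond in either arm

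*Combined protocol and SAP*

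**What the plan says.** All references are to the combined protocol and SAP.

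- **Primary outcome measure.** Of the PPBC: "It is an ordinal scale from 0-5". The best anchor is "My bladder does not cause me any problems at all" and the worst is "my bladder causes me many severe problems". The endpoint is binary: "Patients will be categorized as responders (score improvement by 2 points between screening visit 1 and end of study visit 3) or non-responders".
- **Inclusion criteria, item 2.** The only criterion bearing on severity is "Failure of behavioral measures and/or pharmacologic therapy to adequately control neurogenic bladder symptoms". The objective at the end of the Background names the same population: "patients with neurogenic bladder symptoms that are not adequately controlled with pharmacologic therapy". Neither the two inclusion criteria nor the eleven exclusion criteria mention a PPBC score.
- **Figure 1.** The PPBC is completed at Visit 1, the same visit as the eligibility review and 1 to 4 weeks before randomisation at Visit 2.
- **Sample size.** "we estimate 20% of sham patients and 60% of actively treated patients will be responders". With a chi-square test, two-sided alpha of 0.05 and 80% power, this leads to 27 per group, raised to 30 per group (60 in total) for 10% dropout.
- **Statistical Analysis.** The responder proportions are compared by chi-square test under intention to treat. Nothing restricts or adjusts for baseline PPBC.

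**The concern.** Improvement means a lower score and the scale stops at 0, so the largest possible improvement equals the screening score. A patient who starts at 0 or 1 cannot meet the responder rule however well treatment works. The eligibility rules rely on a clinical judgement about symptom control, whereas the endpoint is the patient's own rating of how much of a problem the bladder is. The two usually agree, but they need not. A score of 0 is hard to reconcile with criterion 2; the realistic case is a patient who scores 1 but is still judged inadequately controlled.

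Each such patient takes one of 60 places and adds no information about treatment to the primary comparison. What is at stake is power and the size of the observed difference. Validity is not affected: randomisation balances these patients in expectation, so neither bias between arms nor type I error inflation follows.

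**Working it through.** **Inputs.** PPBC range 0–5 and the 2-point rule (Primary outcome measure); response rates 20% and 60%, 27 analysed and 30 randomised per arm, two-sided alpha 0.05 (Sample size). The share f of patients screening at 0 or 1 is not in the documents, so a range of 0–20% is shown.

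**Step 1: who can respond.** Maximum improvement = screening score − 0.

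- Score 0: maximum 0 points, cannot respond.
- Score 1: maximum 1 point, cannot respond.
- Score 2: can respond only by reaching 0.
- Score 3 or more: can respond without reaching 0.

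**Step 2: reproduce the planned sample size.** With the pooled-variance formula and a mean rate of 0.40:

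n = [1.96·√(2·0.4·0.6) + 0.842·√(0.2·0.8 + 0.6·0.4)]² / 0.40² = 22.3, so 23 per arm without continuity correction.

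With continuity correction: (22.3/4)·[1 + √(1 + 4/(22.3·0.40))]² = 27.1, in line with the stated 27. Exact enumeration at 27 per arm gives 80.2% power for the corrected test and 86.8% for the uncorrected one. Dropout: 27/0.9 = 30 per arm, as stated. The plan names the chi-square test without saying whether it is corrected, so both versions are shown.

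**Step 3: effect of a share f.** Assume 20% and 60% apply to patients able to respond. The rates in the whole randomised group become 0.20(1 − f) and 0.60(1 − f), and the difference becomes 40(1 − f) points. Power is by exact binomial enumeration; cells show chi-square / continuity-corrected.

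| f | Sham vs active | Difference (points) | Power, 27 per arm | Power, 30 per arm |
|---|---|---|---|---|
| 0% | 20.0% vs 60.0% | 40.0 | 86.8% / 80.2% | 90.5% / 85.1% |
| 2% | 19.6% vs 58.8% | 39.2 | 85.7% / 78.9% | 89.4% / 83.7% |
| 5% | 19.0% vs 57.0% | 38.0 | 84.1% / 76.8% | 87.7% / 81.4% |
| 10% | 18.0% vs 54.0% | 36.0 | 81.2% / 72.9% | 84.6% / 77.5% |
| 12% | 17.6% vs 52.8% | 35.2 | 80.0% / 71.2% | 83.2% / 75.9% |
| 20% | 16.0% vs 48.0% | 32.0 | 74.6% / 63.7% | 77.6% / 69.1% |

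**Step 4: where power reaches 80%.**

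- Uncorrected chi-square: f = 12.0% at 27 per arm (0.12 × 60 ≈ 7 patients) and 16.7% at 30 per arm (10 of 60).
- Continuity-corrected: f = 0.4% at 27 per arm and 6.9% at 30 per arm (about 4 of 60).

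**Step 5: the other reading of the planned rates.** If 20% and 60% already include patients who cannot respond, the plan's power stands as calculated. The rates among those able to respond are then 0.20/(1 − f) and 0.60/(1 − f). At f = 10% that is 22.2% vs 66.7%, a difference of 44.4 points. A floor would then add to the planned difference instead of restoring it.

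**The case against.** The strongest reply is that the calculated loss rests on an assumption the plan does not make. The Sample size section applies 20% and 60% to sham and active patients without restriction and says the calculation is based on intention to treat. The natural reading is that these are rates among everyone randomised, low scorers included. That is a fair reading and possibly the better one. It is not decisive, because the rates are borrowed from earlier percutaneous stimulation work and the documents do not say what endpoint or baseline severity produced them. Nor does it remove the case for a floor: as step 5 shows, excluding certain non-responders widens the expected difference on that reading too.

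Second, f is unsupported and probably small, given inclusion criterion 2. This stands. With the uncorrected test there is slack up to about 12%, or 17% if all 30 per arm are analysed. The slack disappears at 27 per arm only with a continuity-corrected test, which matches the stated 27 but is not named.

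Third, a floor is only a partial remedy and may have side effects. A patient at 2 must still reach 0. Patients at 1 could have contributed to the NBSS, Qualiveen-SF, diary and pad-test endpoints. Selecting on the score that also serves as baseline invites regression to the mean and some inflation of scores near the cutoff. The first two points stand. Regression to the mean weighs less, since dropping patients at 0 or 1 does not alter the outcomes of those at 2 or above. Score inflation is possible and could raise the sham response.

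Finally, choosing a clinical criterion over a score threshold is defensible in a trial the Background calls a pilot. That argues for low weight; it does not show that the gap is absent.

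**Conclusion.** The point holds as a structural observation: the responder rule, the scale and the eligibility list together admit patients who cannot meet the primary endpoint. Its practical size is uncertain and probably modest. The loss of power depends on two things the documents do not give: the share screening at 0 or 1, and whether the planned rates refer to all randomised patients or only to those able to respond. On the less favourable reading, a share of 5% costs 2 points of difference and about 3 points of power at 27 per arm, with either version of the test. This is an inexpensive improvement to consider; the sample size and the primary test are not invalidated by it.

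**What to change.** Add one inclusion criterion: PPBC of 2 or more at screening Visit 1. Every randomised patient can then, in principle, reach the primary endpoint. As a separate clarification, word the responder rule as an improvement of at least 2 points, so that it cannot be read as exactly 2.

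The cost is one eligibility line, with no new data, visit or analysis. Expect a few extra screen failures and a slightly narrower population. Withholding the cutoff from patients would limit score inflation near it.
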